7 MARCH 2025

NCT06213194

Introduction

Nowadays, digital interventions have become more popular day by day to use in different areas including mental health problems, executive functions including working memory (WM), cognitive flexibility and inhibitory control, and social cognitive skills in both clinical and non-clinical populations (Sandgreen et al., 2021). In terms of non-clinical populations, the studies have indicated that executive function training could be effective for both the enhancement of cognitive functions as well as mental health conditions (Beloe & Derakshan, 2020; Sari, et al., 2020). For example, Beloe and Derakshan (2020) have reported that adaptive WM training decreases anxiety and depression symptoms in adolescents and the effects of training lasted for a month. Another study by Roughan and Hadwin (2011) showed that WM training reduces school-related difficulties and associated mental health problems in adolescents. Another study conducted smartphone compassion training for Swedish university students, which resulted in improved self-compassion and emotional awareness compared to the wait-list group (Andersson et al., 2021). Bendtsen and colleagues (2020) developed a mobile health intervention program to promote the mental health of university students. In their randomized control trial (RCT) study, participants showed improvement in positive mental health and reduced depression and anxiety symptoms compared to a control group. Olfers and Band (2018) applied game-based training to improve flexibility and attention and measured in Electroencephalographic (EGG) activity. Their results showed that flexibility and attention show increased performance in healthy young adults compared to the control group. In addition, response selection was improved due to flexibility training. This was indicated by a larger N2 amplitude compared to the control group. Additionally, conflict monitoring was more efficient, as shown by reduced Nc/CRN and larger Pe amplitude (Olfers & Band, 2018). Although studies in Türkiye included both social cognitive training and mental health, which are rare, Sari and colleagues (2020) observed reduced trait anxiety and test anxiety in university students after WM training.

Ben-Zion et al. (2018) have found that cognitive flexibility is a significant predictor of post-traumatic stress disorder (PTSD) and have suggested neurocognitive skills intervention could be an important prevention. Roepke and colleagues (2015) conducted an RCT to examine the effects of smartphone training for depression and depression scores of participants declined after the

training compared to the control group. Similarly, the digital intervention of cognitive behavioral therapy (iCBT) was also shown to be effective in anxiety and depression compared to the control group after 8 weeks of training (Richards et al., 2020). Similarly, smartphone-based CBT was also found to be effective for depression compared to the control group (Lukas et al., 2021). Previous research shows the effectiveness of computer-based social cognitive training in schizophrenia by focusing on emotion recognition, social perception, social discrimination, and theory of mind (Sacks et al., 2013). In other studies, computer-based social cognitive training shows the efficacy of social cognition and social functioning in schizophrenia (Nahum et al., 2021) and the same training program was also effective for ASD and healthy older adults (Nahum et al., 2013). In another study, a randomized control trial (RCT) conducted with ASD participants found an overall improvement in WM, cognitive flexibility, social behavior, ADHD behavior, and quality of life, and the authors suggested a need for further research into the usefulness of cognitive interventions (de Vries et al., 2015). A recent study has shown that game-based cognitive training in school-aged children with ASD provides an improvement in attention, WM, emotion regulation, flexibility, social skills, and communication (Macoun et al., 2021). Moreover, computer-based social cognitive training in adolescents and adults with ASD increases amygdala and fusiform area activation which are associated with facial affect response skills (Bölte et al., 2015). Virtual Reality Social Cognition Training for Autism by Didehbani and colleagues (2016) designed for 5 weeks including emotion recognition, social understanding, and empathy skills shows improvements in emotion recognition, ToM skills, and executive functions. Another digital intervention called the MindChip for socio-emotional skills in autism showed improvements in cognitive empathy and affective empathy skills. A significant difference in self-efficacy, autistic traits, and mental health outcomes was found within the analysis; however, there are no significant differences in self-efficacy, autistic traits, and mental health outcomes between experimental and control groups (Tang et al., 2021). The recent meta-analysis study for digital intervention in ASD by Sandgreen and colleagues (2021) summarized that digital interventions are mostly designed in computer-based format and targeted to social skills. It was found .32 effect size according to Cohen's d , which is a positive but small effect. However, due to the limitation of digital intervention, more studies are needed to see whether these interventions are effective in both clinical and non-clinical populations (Sandgreen et al., 2021) and specifically, there is limited research in Türkiye for digital

mental health intervention to suggest conducting different studies in the recent systematic review by Akgün et al. (2019).

Accordingly, the primary aim of the current study is to test the efficacy of the online training program on mental health (DASS-21 and its subscales) regarding autistic traits. The secondary aim of the current study is to test the efficacy of the online training program on executive functions (working memory, inhibitory control, and cognitive flexibility), and social cognitive skills (cognitive empathy and affective empathy).

The following two hypotheses were addressed in the current study:

- 1. Online training on executive functions and social cognitive skills will promote mental health by reducing DASS-21 and its subscales scores in the current sample.**
- 2. Online training on executive functions and social cognitive skills will promote executive functions (working memory, inhibitory control, and cognitive flexibility) and social cognitive skills (cognitive empathy and affective empathy) in the current sample.**

[figure not shown]
Methods Study Design

The present study adopted a multifactorial design including pretest and posttest conditions to test the efficacy of combined EFs and social cognition online training via computers, tablets, or smartphones for mental health symptoms (depression, anxiety, and stress) in the experimental and control groups. Multifactorial design also called mixed design refers to including both within- participant design (testing the same participants over time) and between-participant design (comparing different groups, Breakwell et al., 2012). The independent variable for this study is online training while the dependent variables are mental health scores (depression, anxiety, and stress symptoms), executive functions (cognitive flexibility, inhibition, and working memory), and social cognition (cognitive empathy and affective empathy). According to our previous findings

(Chapter 4), autistic traits are included in this study as covariates, which are defined by characteristics that might affect the study's outcome (Cambridge University Press, n.d.).

Participants

A power analysis (G*Power) was conducted to determine the number of participants needed to achieve this goal. For repeated measures analyses, 44 participants are required in order to reach a medium effect size of .25 with an adequate power of .80 at $\alpha = .05$ (Faul et al., 2009) to determine interaction effects of between and within participants' factors. Convenience sampling via advertisement through social media, mail groups, and on campuses was used to collect participants. Initially, 178 adult participants were recruited for this study to reach adequate power for multivariate analysis. Participants randomly and equally were assigned to the experimental group (89 participants) and control group (89 participants) to see whether the combined training program was effective for the general population. 33 participants for the experimental group and 48 participants for the control group completed the posttest. However, after checking outliers and normality analysis, 31 participants for the experimental group (28 female, 3 male), and 34 participants for the control group (29 female, 5 male) were included in the further analyses. Please see the figure 6.1. the flow of participants through each stage of the study. The details of the participants were presented the Table 6.1. Demographic Characteristics. To reduce drop-out, incentives such as drawing for money/prizes were used. Inclusion criteria for adult participants are being aged 18 or above, being able to use computers, smartphones, or tablets, being native Turkish citizens, having no record of any psychiatric disorders, and having no record of any physical and neurological conditions that prevent to use of technological devices. Participants who are under the age of 18 and have any record of psychiatric and physical conditions that prevent to use of technological devices were excluded from the study.

Materials

Self-Report Questionnaires

Figure 1. The Flow of Participants

Demographic Information Form

Basic information such as age, gender, education level (i.e., undergraduate, postgraduate), and income was obtained from the participants, and it was developed by the researcher.

Autism Quotient (AQ) for Adults Turkish Version (Baron-Cohen et al., 2006; Baron-Cohen et al., 2001a; Köse et al., 2010)

To measure autistic traits, the Autism Quotient (AQ; Baron-Cohen et al., 2001) was used. AQ for adults is adapted to Turkish culture by Köse and colleagues (2010). The self-report questionnaire consists of 50 questions using a Likert-scale rating; “definitely agree”, “slightly agree”, “slightly disagree”, and “definitely disagree”. In the Turkish adaptation of the AQ for adults, Cronbach’s alpha value for this scale is .64, and test-retest reliability is $r = .72$. The AQ is a widely used assessment tool that measures five subscales: social skills, communication, attention to detail, attention switching, and imagination. It is available in different languages (e.g., Turkish by Köse et al., 2010; Dutch by Hoekstra et al., 2008; Japanese by Wakabayashi et al., 2006).

Depression Anxiety Stress Scale 21(DASS – 21; Lovibond & Lovibond, 1995; Sarıçam, 2018)

DASS-21 is a self-report scale to examine depression, anxiety, and stress levels for adults by Lovibond and Lovibond (1995). The Turkish adaptation study for DASS-21 was conducted by Sarıçam (2018). This scale consists of three subscales, one for depression, one for anxiety, and one for stress. The total number of items is 21. For this scale, inter-scale reliability with Cronbach’s Alpha is .87 for depression, .85 for anxiety, and .81 for stress subscales. Test-retest reliability is $r = .68$ for depression, .66 for anxiety, and .61 for stress.

Performance Tasks

It was administered the following performance tasks to evaluate executive functions such as cognitive flexibility, WM, and inhibitory control, as well as social cognition including cognitive empathy and affective empathy. To ensure standardized measurement, we recorded the errors for each task based on previous intervention studies (Chooi & Logie, 2020; de Vries et al., 2015;

Macoun et al., 2021; Maraver et al., 2016). Each task begins with a non-scored trial to ensure that participants understand the task before scoring begins. The only exceptions are for the self-assessment manikin for affective empathy, and the Eyes Test for which detailed information was provided.

Wisconsin Card Sorting Task (WCST; Berg, 1948)

The Wisconsin Card Sorting Task (WCST) is a cognitive flexibility performance task that was first developed by Berg in 1948. During the task, 200 cards in two blocks are displayed on the screen and the sorting rule changes after every 10 cards. Participants are expected to learn from feedback and adapt the rules during the task by trial and error. They need to match the cards according to their color, number, and shape. The task measures the error rates of the participants. Participants receive feedback only on the accuracy of their sorting, which helps them understand and adjust the current sorting rule. Feedback is given after each card selection.

N Back Task (Kirchner, 1958)

Working memory was evaluated through the N Back Task (Kirchner, 1958) in three different conditions - one back, two back, and three back. In this study, the $n = 2$ rule was applied. A sequence of stimuli was displayed one by one, and participants had to decide if the presented stimuli were the same as the stimuli that appeared in N trials earlier. The complete stimulus sequence consists of 15 letters and each stimulus was displayed for 500 milliseconds. Participants had three seconds to react (3000 milliseconds) and a new letter appeared every three seconds (3000 milliseconds). The letters A, B, C, D, E, H, I, K, L, M, O, P, R, S, and T were used in the sequence. There were eight blocks, with each block containing 50 trials. False errors were measured.

Go / No Go Task (Donders, 1969)

Go / No Go Task was used to measure inhibition. The task requires participants to respond as quickly and accurately as to the presented target stimulus (“go” trials) but avoid responding to non-target stimulus (“no go” trials). Participants need to respond in 2000 milliseconds when the “go” sign is presented and avoid responding when “no-go” is presented. There are 12 blocks of 50 trials each. Commission errors (i.e., incorrectly responding to no-go trials) were measured.

The Eyes Test - for Adults (Baron-Cohen et al. 2001b; Girli, 2014)

The Eyes Test is a performance task for emotion recognition which is widely regarded as an indicator of cognitive empathy. In this test, participants were presented with a series of 36 black-

and-white photographs of human eyes. For each photograph, participants were asked to choose which of 4 words best describes what the person in the photograph is feeling or thinking. The version used was adapted for Turkish by Girli (2014). The Cronbach alpha internal consistency coefficient for this test is greater than .70. Accuracy of the test was measured.

Self-Assessment Manikin (SAM; Bradley & Lang, 1994)

Self-Assessment Manikin was carried out to measure self-reported emotional responses to facial expression images for affective empathy. Karolinska Directed Emotional Faces (KDEF, Conley et al., 2018; Lundqvist et al., 1998) were used to express facial emotions. In total, 30 images (15 male, 15 female) were chosen and seven emotional expressions including happiness, neutral, anger, fear, and disgust were depicted. The task requires participants to examine each facial expression and rate how they feel it on a valence scale (more negative (1) to more positive (9)). The tasks were adapted from Wai and Tiliopoulos (2012). Valence scores for each emotion were obtained by summing responses for all images.

Procedure

Approval from the ethical committee of Ibn Haldun University was obtained for this study (No. E-71395021-050.06.04-34359) and the protocol ID of clinical trials was obtained (NCT06213194). The participants for the study were recruited using convenience sampling through advertisements on social media, mail groups, and campuses. Once recruited, all participants completed pretest questionnaires and tasks before assigning them to the groups and undergoing training on the *MindZone* training website (www.mindzone.com.tr). 31 participants

for the experimental group (28 female, 3 male), and 34 participants for the control group (29 female, 5 male) were included for the study. The experimental group underwent an online 6-week training period through the website developed by the researcher (www.mindzone.com.tr), while the control group was placed on a waiting list. Posttests were collected at the end of the 6th week from both experimental and control groups. Additionally, the researcher and research assistant checked each participant's progress weekly, sent reminder messages, and made phone calls to improve training continuity if participants had not completed the requirements. Details about training are presented in Table 5.2. *MindZone* Manual (see Chapter 5). After the

completion of the research studies, the control group (on the waiting list) is scheduled to access the online training program in accordance with ethical guidelines.

Data Analysis

The data from the current study was analyzed using the SPSS 25.0 package. Initial analyses were performed to determine if the data showed a normal distribution. Before conducting parametric tests, the Shapiro-Wilk test, box plots, and skewness and kurtosis scores were used to check for normal distribution. The self-report questionnaires' data was found to be normally distributed according to the Shapiro-Wilk test ($p > .05$). As for the performance tasks, the skewness and kurtosis of the data fell within an acceptable range for applying parametric tests, as specified by Hair and colleagues (2010). Covariate analyses were conducted to account for the effects of autistic traits in the intervention model. Before including covariates in the analyses, correlation analyses and tests for homogeneity of regression slopes were performed according to the assumptions of covariance (Field, 2013). The results showed that only communication and attention-switching had significant correlations with dependent variables ($p < .05$) and met the assumptions for being used as covariates for mental health symptoms (Field, 2013). Regarding EFs and social cognitive skills, communication, attention to detail and imagination entered as covariates in the model ($p < .05$); however, only communication met the assumptions for homogeneity of regression slopes for EFs and social cognitive skills (Field, 2013). All correlation tables for these assumptions were presented in Appendix C, D, and E. Moreover, t-test analysis was carried out to see whether the pretests of dependent variables and AQ and its subscales for experimental and control groups

differ. Due to more than 8 variables; a conservative p -value was set ($p = .01$). The results showed no significant differences in all pretest scores and AQ (all $ps > .01$).

In the experimental study, 2 x 2 mixed design repeated measure ANOVAs were conducted to examine the group (experimental and control group) and the effects of time (pretest and posttest) on mental health (DASS-21 and its subscales), as well as executive functions (working memory, inhibitory control, and cognitive flexibility), and social cognitive skills (cognitive empathy and affective empathy). In terms of performance tasks, to ensure standardized measurement, errors

were used in the analyses for each EF task based on previous intervention studies (Chooi & Logie, 2020; de Vries et al., 2015; Macoun et al., 2021; Maraver et al., 2016). While accuracy was used for cognitive empathy and summing scores of images in affective empathy entered as dependent variables.

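### The sample-size target is an unjustified 1.0 SD difference in change; the 65 analysed have low power for smaller effects, and adjusting for the pretest would recover precision at no data cost

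*Combined protocol and SAP*

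**What the plan says.** Under Methods, Participants, the G*Power statement is that "44 participants are required in order to reach a medium effect size of .25 with an adequate power of .80" at alpha .05, for the between-by-within interaction. It gives no pre-post correlation, no effect-size option and no reason for choosing .25.

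The same section continues: "Initially, 178 adult participants were recruited for this study to reach adequate power for multivariate analysis". Of these, 89 were assigned to each arm. Then "33 participants for the experimental group and 48 participants for the control group completed the posttest", and after outlier and normality checks "31 participants for the experimental group (28 female, 3 male), and 34 participants for the control group" entered the analyses.

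Data Analysis gives the test: "2 x 2 mixed design repeated measure ANOVAs were conducted to examine the group" and time effects on DASS-21 and its subscales, among other outcomes. The covariates named for mental health are two AQ subscales, communication and attention-switching. The pretest of the outcome is not named as a covariate.

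The Introduction reports one numerical effect size, from a meta-analysis of digital interventions in autism: "It was found .32 effect size according to" Cohen's d, "which is a positive but small effect".

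**The concern.** For a 2 x 2 interaction, f = .25 has no fixed clinical meaning until the effect-size definition is stated. On the definition that returns 44 it is a full standard deviation of between-arm difference in change. That is a demanding target for DASS-21 in adults selected for having no psychiatric record, and nothing in the documents argues for it.

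If the true benefit is well below 1.0 SD, the primary analysis will probably miss it. A non-significant interaction could then be taken as evidence of no benefit because the trial is described as adequately powered. The chosen test also gives up precision: it compares change scores, although a pretest taken before assignment is available for direct adjustment.

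**Working it through.** **Inputs from the documents.** f = .25, power .80, alpha .05, N = 44, 31/34 analysed and 33/48 with a posttest (Participants); DASS-21 subscale test-retest r of .68, .66 and .61 (Materials); d = .32 (Introduction).

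**Assumptions.** The pre-post r is not reported. I use .35 (implied by N = 44), .5, .61 and .68 (the ends of the DASS-21 subscale retest range), with .80 as a further check. Power figures leave out the AQ covariates.

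**1. Reproducing 44.** F test with df = (1, N - 2).
- Cell-mean definition: noncentrality = f² x N x 2/(1 - r). At r = .35 and N = 44 this is .0625 x 44 x 2/.65 = 8.46, and power is .811. The smallest even N reaching .80 is 44 for r = .332 (power at 44 is .8005) to .363 (power at 42 is .7999). At r = .5 the required N would be 34; at r = 0 it would be 66.
- The other two definitions, with noncentrality f² x N or f² x (N - 2), need 128 and 130 whatever r is.

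So 44 comes only from the cell-mean definition with an unstated r of about .33 to .36.

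**2. What f = .25 means there.** The four cell interaction effects are ±(difference in change)/4, so the difference in change = 4 x f = 4 x .25 = 1.0 outcome SD, independent of r. On the same scale 0.32 SD is f = .08, and 1.0/.32 = 3.1.

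**3. Is the stated power met?** Yes. For 1.0 SD, 31/34 gives 93.5% at r = .35 and more at higher r.

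**4. Power and precision at 0.32 SD, 31/34.** √(1/31 + 1/34) = 0.248.
- Group x time ANOVA (equivalent to a t test on change): SD of change = √(2(1 - r)), df = 63, 95% CI half-width = 1.998 x 0.248 x √(2(1 - r)).
- ANCOVA on the pretest: residual SD = √(1 - r²), df = 62, half-width = 1.999 x 0.248 x √(1 - r²).
- Variance ratio, ANCOVA to ANOVA: (1 - r²)/(2(1 - r)) = (1 + r)/2, which is below 1 whenever r < 1.

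| r (assumed) | .35 | .50 | .61 | .68 |
|---|---|---|---|---|
| Power, ANOVA | 20% | 25% | 30% | 35% |
| Power, ANCOVA | 27% | 31% | 36% | 41% |
| CI half-width, ANOVA (SD) | 0.57 | 0.50 | 0.44 | 0.40 |
| CI half-width, ANCOVA (SD) | 0.47 | 0.43 | 0.39 | 0.36 |
| Variance ratio | .675 | .75 | .805 | .84 |

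At r = .80 the ANOVA has 52% power. It reaches 80% only at r of about .90. Every half-width in the table exceeds 0.32, so an estimate of zero would not exclude 0.32 SD under either test.

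**5. All 81 completers (33/48), ANCOVA, df = 78.** With the SD unchanged, power at 0.32 is 32%, 37%, 42% and 48%. With the SD 10% larger (an assumption) it is 27%, 31%, 36% and 41%, the same as ANCOVA in the 65. With the SD 20% larger it is 24%, 27%, 31% and 36%.

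**The case against.** The strongest reply is that the plan claims .80 power for f = .25 and nothing else, that medium is the customary label for that value, and that 65 analysed exceeds 44. All of that stands.

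A reader might infer that the target contradicts the plan's own evidence, because 1.0 SD is about three times the d = .32 in the Introduction. The documents do not support that. The .32 comes from autism studies mostly aimed at social skills, the plan never adopts it as a planning effect, and its standardisation is not described. The mental-health studies cited in the Introduction carry no effect sizes. The documents therefore neither support nor contradict 1.0 SD on DASS-21. For the same reason, rebasing the sample size on .32 after the data are in would replace one rationale with another that was not used.

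The 20% to 35% range also depends on assumptions. The lower end uses a correlation back-solved from N = 44. The DASS-21 subscale values alone give 30% to 35%. No retest figure is given for the DASS-21 total, so .68 is not an upper bound.

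Finally, changing the test and the analysis set after data collection has a cost, and those removed in outlier and normality checks may well bring a larger SD with them. Both points stand and shape the fix. They do not affect the precision gain from pretest adjustment within the same 65 people.

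On 178, recruiting above a minimum of 44 is not a contradiction, and the word multivariate may be meant loosely. The missing calculation is a reporting gap.

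**Conclusion.** The concern holds in limited form. The power statement is reproducible for a 1.0 SD difference in change once an unstated r of about .33 to .36 is supplied. That target is optimistic and has no stated justification. For a 0.32 SD difference, used only as a benchmark, the planned test in 31/34 has about 20% to 35% power for r from .35 to .68, and 52% at r = .80.

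The actionable part is the choice of test. ANCOVA on the pretest uses data already held and adds about 5 to 7 percentage points of power at 0.32 SD. It cuts the CI half-width by 0.03 to 0.10 SD, most when r is low. Power remains well short of 80% over r = .35 to .68, so conclusions should rest on the estimate and its interval. These figures assume equal SDs at the two time points and in the two arms, and no AQ covariates.

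**What to change.** 1. For each primary DASS-21 outcome (total and subscales), replace the 2 x 2 group x time ANOVA with ANCOVA of posttest on group, adjusted for the pretest of the same measure alongside the AQ covariates already planned. The Procedure section places the pretest before assignment, so it is a proper baseline covariate.
2. Run the same model in all 81 participants with a posttest (33/48) as well. Do not promise a power gain from this step: it disappears if the SD is 10% larger.
3. Report the between-arm difference with its 95% CI, and do not describe a non-significant result as showing no effect.
4. As minor reporting points, keep the original sample-size rationale but add the r and G*Power option behind 44, the reason for f = .25, and the basis for 178 (or drop the reference to multivariate analysis).

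Cost: no new enrolment or data, only a re-run of the primary models and a revised paragraph. The real drawback is that the primary test changes after data collection. The original ANOVA should therefore be shown beside the ANCOVA, and the change stated openly.

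### The only efficacy analysis described uses 65 of 178 randomised participants, after two selection steps that were unequal between arms; no removal rule or missing-data analysis is stated, and the size and direction of bias are unknown

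*Combined protocol and SAP*

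**What the plan says.** Methods, Participants, states that 178 people were assigned at random and equally, 89 to training and 89 to the waiting list, "to see whether the combined training program was effective for the general population". It then gives two reductions. First, "33 participants for the experimental group and 48 participants for the control group completed the posttest". Second, "However, after checking outliers and normality analysis, 31 participants for the experimental group" and 34 for the control group were carried into all further analyses.

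Data Analysis names the checks: "the Shapiro-Wilk test, box plots, and skewness and kurtosis scores were used to check for normal distribution". It gives no threshold for removing a person, and does not say which variable or which time point led to a removal. The efficacy analyses are 2 x 2 (group x time) mixed ANOVAs, with autism-trait subscales considered as covariates. No all-randomised set, missing-data method or sensitivity analysis is described.

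Procedure says that "all participants completed pretest questionnaires and tasks before assigning them to the groups", then gives 31 and 34 as the participants included. Attrition is met only by prevention: prize draws (Participants), and staff who checked each person's "progress weekly, sent reminder messages, and made phone calls to improve training continuity" (Procedure).

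The flow figure is not shown, and Table 6.1 and Appendices C to E are not in the file. They may give reasons for loss or removal.

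**The concern.** Randomisation makes the arms comparable for the 178, not for a subset chosen afterwards. Here there are two such choices. More people were lost from training, and more completers were removed from control. Because they pull in opposite directions, the final counts of 31 and 34 hide the imbalance, and a reader who sees only those counts would suspect nothing.

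The removals are the more avoidable step. Those 16 people had completed the posttest, 14 of them were in one arm, and no rule is given that would let a reader reproduce the choice. One reduced set also serves every outcome, so the text does not exclude that an extreme score on one task cost a person their DASS-21 data, which is the primary aim.

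At stake is whether a group x time effect, or its absence, reflects the training or the selection.

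**Working it through.** **1. Counts (inputs from Methods, Participants).** The plan's own figures agree internally: 89 + 89 = 178; 28 + 3 = 31; 29 + 5 = 34; 31 + 34 = 65.

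| Step | Training | Control | Difference (Wald 95% CI) | Fisher p |
|---|---|---|---|---|
| No posttest | (89 - 33)/89 = 56/89 = 62.9% | (89 - 48)/89 = 41/89 = 46.1% | 16.9 points (2.4 to 31.3) | 0.035 |
| Removed, of completers | (33 - 31)/33 = 2/33 = 6.1% | (48 - 34)/48 = 14/48 = 29.2% | 23.1 points (7.9 to 38.3) | 0.011 |
| Analysed, of randomised | 31/89 = 34.8% | 34/89 = 38.2% | 3.4 points | 0.76 |

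Overall, 97/178 (54.5%) have no posttest, 16/81 (19.8%) of observed posttests were set aside, and 65/178 (36.5%) were analysed.

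**2. What the removals could do to the planned test.** With two time points, the group x time test is the change contrast: mean (post - pre) in training minus the same in control. Assumptions: no true effect, normal scores, random completion (33 and 48), then removal of 2 and 14. The pre-post correlation r is .61 to .68, the DASS-21 retest range in Materials (.68 "for depression, .66 for anxiety, and .61 for stress"). Results come from simulations of 4,000 runs per setting, and a 6,000-run repeat agreed within simulation error and supplied the rows marked *.

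| Who is removed | Bias in change, SD | Type I error |
|---|---|---|
| Nobody (all 81 kept) | about 0 | 4.9% to 5.2% |
| Random | about 0 | about 5%* |
| Largest absolute posttest, or largest absolute value at either time (r = .65) | -0.002 | 5.1% to 5.2% |
| Highest value at either time | about 0 | about 5%* |
| Highest posttests | +0.11 to +0.14 | 9.5% to 10.4% |
| Lowest posttests | -0.12 to -0.14 | 9.6% to 10.1%* |
| Highest pretests | -0.12 to -0.15 | 9.6% to 10.4%* |

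DASS-21 and the executive-function error scores improve downwards, so a positive value counts against training and a negative one favours it. Removing high posttests, mostly from control, would bias against training. Removing low ones would favour it.

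**3. Dropout.** The mechanism is unknown. Under assumed mechanisms with no removals, dropout that depends on pretest moves the change contrast by 0.03 to 0.20 SD, and a pretest-adjusted ANCOVA on the same completers is about unbiased. A stable trait that drives dropout in training only leaves the change contrast at about 0, but moves both the ANCOVA and a mixed model on all 178 by 0.08 to 0.17 SD. No single model is safe under both.

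**4. Do the pretest comparisons settle it?** Data Analysis reports: "The results showed no significant differences in all pretest scores and AQ" (threshold .01). The text does not say whether these t-tests used 178 or 65, and they compare arms, not completers with non-completers. With 31 vs 34, power at .01 is 8%, 27% and 71% for pretest gaps of 0.30, 0.50 and 0.80 SD.

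**5. Precision if the 16 are kept.** SE of the change contrast = SD x sqrt[2(1 - r)(1/n1 + 1/n2)]. At r = .65, sqrt[0.70 x (1/31 + 1/34)] = 0.208 SD and sqrt[0.70 x (1/33 + 1/48)] = 0.189 SD. The ratio is 0.911, a gain of about 9% if the SD does not change.

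**The case against.** The strongest reply is that unequal removal counts do not by themselves bias the comparison. Box plots flag both tails, and two-tailed removal gives about 0 bias in the planned test. Material bias needs one-directional removal tied to the analysed outcome, and nothing in the text shows that. With many outcomes screened the link weakens further: removing people with the highest posttest on any of nine outcomes (assumed independent, r = .65) gives 0.026 SD and 5.7% type I error. This stands, and it is why no size can be claimed.

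Three stronger readings that a reader might infer are not supported:
- *A type I error near 30%.* Figures of 29% to 33% arise only for a pretest-adjusted ANCOVA after removal of the highest posttests. The plan describes mixed ANOVAs with autism-trait covariates, not that model.
- *Removals that favoured training, or were chosen from posttest values.* Removal is reported after posttest completion, but that is reporting order and does not show what triggered it. The sign could go either way.
- *An unqualified claim about everyone.* Participants mentions the general population, which may simply mean non-clinical. Both hypotheses in the Introduction are confined to the current sample, and convenience sampling limits generalisation in any case.

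It could also be said that 65 exceeds the 44 in the power calculation. That concerns power: at f = .25, 65 people give about 0.80 to 0.98 for correlations of 0 to 0.5. It does not answer a question about selection. Nor do the missing figure and appendices. They may explain the losses, but the Data Analysis text is visible and describes no analysis that deals with them.

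**Conclusion.** The point holds as a defect of the analysis set, and it should be fixed before any efficacy conclusion is drawn. The counts come straight from the plan: 65/178 analysed, loss of 62.9% vs 46.1%, and removals of 6.1% vs 29.2% with no stated rule. The similar final arm sizes are the net of two unequal steps and give no reassurance.

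The size and direction of bias are unknown. For the planned change test the removals could matter not at all (random or two-tailed) or by about 0.11 to 0.15 SD in either direction with type I error about 10% (one-tailed on the pretest or posttest of the analysed outcome). Those figures assume no true effect, random completion and r of .61 to .68. Bias from dropout would come on top and cannot be sized from the documents. The finding rests on the unequal, rule-less selection, not on a demonstrated distortion of the result.

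**What to change.** 1. Make the main analysis a comparison by assigned group with all 81 observed posttests kept. Handle non-normality with robust or permutation methods rather than by removing people. State the removal rule (cut-off, variable, time point), and show the 65-person result only as a sensitivity analysis.
2. Confirm that usable pretests exist for the 97 non-completers, because Procedure says that all completed pretests but then counts 31 and 34 as included. Then add an all-randomised analysis (mixed model or multiple imputation) with a delta or reference-based variant. Present these as sensitivity analyses that rest on untestable assumptions, not as a cure.
3. Report pretest scores, autism-trait scores and demographics, by arm, for completers, non-completers and the 16 removed, with reasons for loss where known.
4. Limit conclusions from the 65 or the 81 to completers.

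Cost: more analysis and reporting, with no new data collection. Retained outliers may widen the SD and offset the roughly 9% gain in SE from using 81 instead of 65.
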